### 8.2 SAFETY ASSESSMENTS

The PHQ-9 administered at baseline, 3-, 6-, and 12-month time points will be used to assess suicide risk. A positive answer to a PHQ-9 question “Over the last 2 weeks, have you had thoughts that you would be better off dead or of hurting yourself in some way?” will trigger the Scale for Suicide Ideation questionnaire developed to determine the level of immediate suicide risk. Individuals who are not affiliated with one of the participating clinical sites and are completing the Web questionnaires will only receive the PHQ-8 and will not be assessed for suicidality.

*To read more about this risk management protocol, go to **Section 2.3.3. Assessment of Potential Risks and Benefits.***

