In the first three months of the study, intervention participants will complete all modules of their assigned study arm (cCBT or m-Education) at their own pace. The recommended progression is one module per week; this will give participants time to practice the techniques taught in each module. Participants will be asked to complete a daily electronic diary to track their pain symptoms.

Only intervention arm participants will receive follow up assessment. The convenience comparison group will not be followed with scheduled assessments.

**1st Follow-Up (T1).** At the end of month 3 (i.e., three months after enrollment, on the same date the participant began the study) participants will again receive a link to our online survey tool to complete the second iteration of Painimation, the SCSS, PROMIS, ASCQ-ME, PHQ-9, and GAD-7. If participants have questions while completing these questionnaires, they may contact their health coach for guidance. Participants will also be asked to complete daily pain intensity entries in the electronic diary. If participants do not complete the questionnaires or the pain intensity entries, health coaches will contact them and remind them to do so. The 48 patients selected for qualitative interviews will have their second interview with Qual-EASE at this time.

Between months 4-6, participants will continue to log their daily pain diary in the CaRISMA intervention but will no longer be expected to have weekly check-ins with their health coach.

**2nd Follow-Up (T2).** At the end of month 6, participants will receive a link to our online survey tool to complete Painimation, SCSES, PROMIS, ASCQ-ME, PHQ-9, and GAD-7 for the third time. Note: participants will not complete the COMM at T2. Though scheduled weekly check-ins with health coaches will have ceased, participants will still have the opportunity to contact their health coach as needed. Participants will continue to complete daily pain intensity entries through the electronic diary.

Between months 6-12, participants will continue daily pain diary submissions and communication with health coaches as needed. Additionally, Qual EASE will conduct the final set of qualitative interviews with the 48 randomly selected participants.

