**3rd and final Follow-Up (T3).** In the final month of the study (T3), participants will receive a link to our online survey tool to complete Painimation, SCSES, PROMIS, ASCQ-ME, PHQ-9, GAD-7, and COMM for the final time.

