**Medical Outcomes (PCORnet).**

For patients recruited at one of the five clinical sites, we will evaluate objectively measured opioid medication refills and emergency department visits or hospitalizations for pain crisis. We will be working in collaboration with PCORnet to collect data retrospectively (from the past 12 months) and prospectively (12 months from date of enrollment) from patient medical records. These data will allow us to track medications including opioid pain medication prescriptions and refills, and health care utilization (i.e., emergency department visits and

hospitalizations), as well as lab values (e.g., hemoglobin level) and clinical outcomes (e.g., end-organ damage score). For the patients recruited from our community partner organizations or online who are not affiliated with a participating clinical center, we will only acquire or evaluate their medical records for the purpose of confirming their sickle cell diagnosis.

**Process evaluation measures.** For the intervention to be effective, patients must use the program and acquire coping skills or knowledge about pain and SCD that will help them manage their physical health (e.g., nutrition/exercise), emotional distress, and physiological response to stressors, all factors contributing to pain. As they progress through the intervention, participants will complete elements of the Coping Strategies Questionnaire for sickle cell disease (CSQ) and the Sickle Cell Self-Efficacy Scale (SCSES) shown in **Figure 6**.

1) How sure are you that you can do something to cut down on most of the pain you have when having a pain episode?	Not at all sure	Not sure	Neither	Sure	Very Sure
2) How sure are you that you can keep doing most of the things you do day-to-day?	Not at all sure	Not sure	Neither	Sure	Very Sure
3) How sure are you that you can keep sickle cell disease pain from interfering with your sleep?	Not at all sure	Not sure	Neither	Sure	Very Sure
4) How sure are you that you can reduce your sickle cell disease pain by using methods other than taking extra medication?	Not at all sure	Not sure	Neither	Sure	Very Sure
5) How sure are you that you can control how often or when you get tired?	Not at all sure	Not sure	Neither	Sure	Very Sure
6) How sure are you that you can do something to help yourself feel better if you are feeling sad or blue?	Not at all sure	Not sure	Neither	Sure	Very Sure

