### *Pre-screen Chronic Pain Questions*

Patients who do not meet criteria 4 and 5 will only complete the battery of questionnaires at baseline and each time they return to clinic for a medical visit. This is a convenience comparison sample of non-chronic pain patients and there will not be scheduled follow-up with this group.

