##### Online recruitment through community partners:

Our CBO partners have created an active community that reaches 10000+ patients with SCD. For this study SC101, SCWarriors, and SCCC will seek out potential participants via message blasts on their CBO websites, social media groups, email listservs, and at patient/family meetings. SCWarriors has a unique database of over 550 people who have signed up specifically to participate in clinical research. Interested patients will access a short online screener on a mobile device to confirm eligibility. To be eligible, potential participants must be able to read the study consent and correctly answer comprehension questions (our group is currently using and has published data using this electronic consent process in a clinical study and a large multisite trial of cCBT). [name] (co-I) will lead online recruitment efforts through SC101. [name], will promote the study through SCWarriors, and [name], will promote the study through the SCCC network of CBOs.

Once participants finish the initial screener and are approved to be enrolled, they will be complete consent procedures as outlined in the **Consent Procedures and Documentation**. After consenting, they will be assigned a health coach, linked to the study-associated Facebook page, and will receive instructions on how to access the CaRISMA intervention to begin their intervention arm.

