### 6.3 MEASURES TO MINIMIZE BIAS: RANDOMIZATION AND BLINDING

**Randomization:** Participants will be randomized in an equal fashion (1:1) to both study arms. Random permuted block randomization will be used to create an allocation list that will be integrated within our Web-based data entry system. Stratification will be based on recruitment site (Pitt, Duke, Hopkins, OSU, UIC) or through one of the community partners (SC101, SCCC, and Sickle Cell Warriors).

**Reduce the potential for biases.** The introduction to both interventions will look identical and participants will not be told what type of training they are receiving. We will make every effort to mask the intervention type; however, as with all behavioral interventions, completely blinding participants to the intervention is challenging. The investigative team will continue to maintain clinical equipoise regarding the comparative therapeutic merits of each treatment. Randomization will avoid selection bias as well as volunteer or referral bias. A dropout analysis will be carried out to determine the contribution of attrition bias. All outcomes measures will be collected electronically, without an interview, to avoid expectation bias. We have also found this mode of data collection to be superior to assessments by phone for timely follow-up. Finally, we will avoid participant recall or memory bias by asking patients to record daily pain, fatigue, and other health outcomes via mobile device.

To limit potential bias from investigators, we are implementing a dual PI plan that separates data collection, monitoring, and analysis from the day-to-day implementation of the study interventions and engagements with community partners who can influence the outcomes of the trial. Broadly put, [name] will be primarily responsible for stakeholder and community engagement and the scientific/clinical aspects of this trial, while [name] will be responsible for the data and statistical analysis of the trial. In addition to limiting bias, we believe that due to the intensive plan we have outlined for stakeholder and community engagement, the overall project benefits from having a PI ([name]) who is dedicated to this role and who has less responsibility for data oversight.

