Cognitive Behavioral Therapy and Real-Time Pain Management Intervention for Sickle Cell Via Mobile Applications (CaRISMA)

NCT04419168

1/13/2023

Statistical Analysis Plan

Study Design & Objectives. CaRISMA is a multisite, randomized, pragmatic, comparative effectiveness trial that will be conducted at 6 comprehensive sickle cell centers and 4 community-based organizations (CBOs). A total of 350 adults with SCD who report chronic pain and/or use long acting or daily opioids will be enrolled and randomized in a 1:1 ratio to receive either a digital CBT program tailored for adults with SCD (CBT) or pain and SCD education (Education) on their mobile phones for 12 weeks. Both programs will use identical mobile-based technology platforms, with the only difference being the content provided. The focus of the digital CBT program is to teach behavioral coping skills through participants' seeing and doing, whereas the pain education arm focuses on improving self-management through participants' learning and knowing more about pain and SCD.

The primary objective of the CaRISMA (Cognitive Behavioral Therapy and Real-time Pain Management Intervention for Sickle Cell via Mobile Applications) trial is to compare the effectiveness of two mobile phone-delivered programs for reducing SCD pain symptoms at the 6-month follow-up: digital CBT versus pain and SCD education (Education). We will also evaluate the sustainability of the intervention effects at the 12-month follow-up. The secondary objective is to assess whether baseline depression symptoms moderate the effect of interventions on pain outcomes. We hypothesize that digital CBT will confer greater improvement in pain interference, pain intensity, and depressive symptoms at 6 months compared with Education. We also hypothesize that digital CBT will confer a greater reduction in health care use (e.g., opioid prescriptions or refills or acute care visits) over 12 months compared with Education.

Randomization. Upon completion of eligibility, participants will be randomly assigned to either digital CBT or Education. Permuted block randomization will be stratified by study center (e.g., one of the six clinical sites or from a community partner) in an effort to control for site-specific disease education and treatment approaches. The randomization schema was created by the lead statistician in the data coordinating center and integrated into the web-based data capture system.

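### Does giving the PHQ-8 to unaffiliated web participants leave the plan's PHQ-9 depression analyses undefined?

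*Protocol*

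**What the plan says.** Protocol 8.2 (Safety Assessments) contains the only mention of the PHQ-8 in either document: "Individuals who are not affiliated with one of the participating clinical sites and are completing the Web questionnaires will only receive the PHQ-8". The same sentence adds that this group is not assessed for suicidality. Elsewhere the protocol describes the PHQ-9 without that exception. For month 6, for example, section 4.1 says "participants will receive a link to our online survey tool to complete Painimation, SCSES, PROMIS, ASCQ-ME, PHQ-9, and GAD-7 for the third time".

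The SAP defines one depression score, nine items rated 0 to 3 with a total of 0 to 27. It uses that score in three places:

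- as a baseline covariate (at most 10 versus above 10) in the mixed models for the primary and secondary outcomes, and in the health care utilization models;
- as the moderator in the Subgroup Analysis;
- as the outcome for H2.

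Under Analysis Sets, the SAP includes everyone randomised.

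On who might be affected, Protocol 5.5 says of people recruited online that they "will receive instructions on how to access the CaRISMA intervention to begin their intervention arm". The PCORnet paragraph of Protocol 4.1 refers to a similar group: "For the patients recruited from our community partner organizations or online who are not affiliated with a participating clinical center". Protocol 6.3 and the SAP's Randomization paragraph both count the community partners in the stratification.

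**The concern.** A nine-item total cannot be computed from eight items. If some randomised participants complete only the PHQ-8, then, read literally, the SAP leaves them without a baseline depression class and without an H2 outcome. A mixed model drops a record with a missing covariate, so these people could leave even the primary analysis, against the SAP's own intention-to-treat statement. The SAP's missing-data section does not help. It deals with dropout and missing outcomes, not with a shorter form of a baseline scale.

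If the scores are kept, the analyst must choose between raw pooling, proration and a common eight-item score. These rules do not all place the cut at the same point. At stake would be the reproducibility of the moderator and of H2, and possibly some loss of sample.

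**Working it through.** **Who is affected.** The passages point both ways.

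- *Randomised participants:* Protocol 5.5, 6.3 and the PCORnet paragraph show that people recruited online can be randomised and that some have no tie to a clinical site.
- *Non-randomised enrolees:* Protocol 5.4 says people who enrol but do not qualify for an arm complete a baseline questionnaire only, and it mentions no clinic visit. The Baseline text in 4.1 also implies that people outside the randomised group fill in the baseline battery. An unaffiliated web enrolee without chronic pain fits the wording of 8.2. Against this, Protocol 5.1 says the comparison sample "will only complete the battery of questionnaires at baseline and each time they return to clinic for a medical visit", which suggests clinic patients.
- *Dates:* the protocol is dated 6/15/2020 and the SAP 1/13/2023. The later document lists the PHQ-9 at every assessment, so the exception may no longer apply.

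The ceiling comes from Protocol 5.6, Table 5, which plans 50 community or online enrolments among 350: 50/350 = 14.3%. Anyone in that 50 who attends a participating site falls outside the exception. The figure belongs to a plan with five sites and three community partners; the SAP has six and four.

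**Scale.** Nine items × 3 = 27, which reproduces the SAP's range. Eight items × 3 = 24.

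**Where the cut falls under each rule**

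| Eight-item sum | Raw sum > 10? | × 9/8 | Unrounded > 10? | Rounded > 10? | Item 9 needed for a nine-item total > 10 |
|---|---|---|---|---|---|
| 8 | no | 9 | no | no | 3 |
| 9 | no | 10.125 | yes | no (10) | 2 or more |
| 10 | no | 11.25 | yes | yes (11) | 1 or more |
| 11 | yes | 12.375 | yes | yes (12) | none |

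The rules disagree with one another only at sums of 9 and 10. Against the true nine-item total, the raw sum changes class in six combinations of sum and item 9: (8,3), (9,2), (9,3), (10,1), (10,2) and (10,3).

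**How many people that could be.** The documents give no score distribution. Assume 10% to 30% of the 50 have sums of 8 to 10, and 5% to 30% of those endorse item 9. Raw scoring then misplaces between 50 × 0.10 × 0.05 = 0.25 and 50 × 0.30 × 0.30 = 4.5 people.

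**H2 under raw pooling.** Assume the effect is spread evenly over nine items. An eight-item score then carries 8/9 of it, and the overall dilution is (50/350) × (1/9) = 1.6%.

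**Bias between arms.** The form follows affiliation, which is fixed before randomisation. Randomisation is stratified by centre or community partner, and study site is in the models. No differential effect on the arms is expected under any of these rules.

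**Outer bound if all 50 were dropped.** The SAP's intention-to-treat statement rules this out, so it is not the expected handling. Take 0.37 SD and 15% attrition from the SAP's sample size paragraph, and assume a two-sided 0.05 test. Power = Φ(0.37 × √(n/2) − 1.96), with n per arm.

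- All 350: n = 350 × 0.85/2 = 148.75, power 89.1%. The SAP states 80% for these inputs, so its figure does not reproduce with this formula; the difference is on the cautious side.
- 300 kept: n = 300 × 0.85/2 = 127.5, power 84.0%.

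I give no power figure for the subgroup interaction. Protocol 9.2 already concedes that it would need about 1,400 participants.

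**The case for a change.** The case for a written rule is fair. The natural reading of 8.2 does reach some randomised participants, since the protocol elsewhere speaks of community or online recruits without a clinical centre and randomises people recruited that way. The score has three roles, including a covariate in the primary model. Nothing in the SAP tells the analyst what to do, so two analysts could classify sums of 9 and 10 differently. A sentence on scoring would be cheap, and items 1 to 8 are on both forms.

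What stands is that the documents do not say who received which form and give no eight-item rule. What does not stand is that this endangers a result. Departing from a general description for one group is an exception, and not every passage that omits it is a contradiction; Protocol 6.1.2 says only that the follow-up battery can include the PHQ-9.

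A common eight-item score for everyone also has a price. It sets aside the prespecified total for all 350 because at most about 50 may lack one item, so class changes at sums of 8 to 10 could occur in seven times as many people (350/50). The standardised H2 effect would be multiplied by (8/9)/√((8+56r)/(9+72r)), where r is the inter-item correlation of change. For r of 0.2 to 0.6, with equal item variances and an even effect (all assumed), that is 0.981 to 0.996. Power moves from 89.1% to between 87.9% and 88.8%. Proration for the affected few avoids this but needs a rounding convention. Reasonable statisticians would differ on the choice.

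**Conclusion.** The observation is correct, but it is a gap in detail that analysts can fill sensibly. The intention-to-treat statement already tells them to keep every randomised participant, which leaves only a choice among close scoring rules, made without regard to arm and reported with the results. For the primary contrast, depression is only a baseline adjuster.

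The expected consequences are no bias between arms, a depression class that can change only at eight-item sums of 8 to 10, and about 1.6% dilution of the H2 effect under the crudest handling. Even the excluded worst case keeps primary power at 84.0%, above the stated 80%.

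This rests on the planning ceiling of about 50 short-form participants, on an effect spread evenly over items, and on a two-sided 0.05 test. A much larger share of unaffiliated participants would raise the H2 dilution in proportion but would not create bias between arms. No position is taken on item 9 or on the safety procedures.

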## 8.3 ADVERSE EVENTS AND SERIOUS ADVERSE EVENTS

The following definitions are taken directly from Rozental et al 2014, which addresses Internet interventions, and Linden 2013, which discusses the negative effects in face-to-face behavioral treatment.

**Deterioration** \*\*detail here, only mentioned in passing in 5.13 osiris\*\* Items marked \*\*\* below not in osiris  
Deterioration is defined as worsening of target symptoms and monitored by a validated outcome measure or behavioral measure, i.e., an increase of symptom severity, or increased frequency of intrusive thoughts. In order to distinguish temporary from enduring deterioration, we will rely on consecutive measures and follow-up. Weekly check-ins by the health coach during treatment, e.g. "Do you feel like your pain or mood is worsening?", administration of the PHQ-9 or the numerical pain scale. The health coaches will be trained to assess for negative/intrusive thoughts. The PHQ and pain scale will be administered post-treatment at 3-month, 6-month, and 12-month follow-up. Post-treatment data will be routinely analyzed each month for unexpected deviations from expected, e.g. greater than a standard deviation increase in pain or depressive symptoms. The exact alert threshold will be determined based on baseline distribution of study data.

### Adverse events

Adverse events (AEs) consist of negative events probably emerging from treatment and perceived as adverse by the patient, causing deterioration of target symptoms and/or negative experiences that extend beyond the completion of treatment, e.g., increased anxiety during cognitive behavioral therapy training, or being embarrassed by revealing negative thoughts and insecurities to the health coach. Adverse events could reveal negative effects that are directly attributable to treatment, providing our team and other researchers with information on possible mechanisms underlying negative effects. During treatment, the health coaches will routinely assess for increasing negative affect. Post-treatment, the GAD-7 will be administered at 3, 6, and 12 months to assess for increasing anxiety.

\*\* In Osiris 5.13 , also unexpected problems (UPs), medical monitor, timing of reporting.\*\*

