## 7 STUDY INTERVENTION/EXPERIMENTAL MANIPULATION DISCONTINUATION AND PARTICIPANT DISCONTINUATION/WITHDRAWAL

### 7.1 DISCONTINUATION OF STUDY INTERVENTION/EXPERIMENTAL MANIPULATION

Semi-annually, the DCC and Data Safety Monitoring Board (DSMB) will review of collected data (including adverse events, unanticipated problems, and subject withdrawals), to determine whether there is a change to the anticipated benefit-to-risk assessment of study participation and whether the study should continue as originally designed, should be changed, or should be terminated.

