### Severe adverse events

Severe adverse events (SAEs) are negative events that occur during treatment and result in deterioration of target symptoms and/or adverse reactions requiring some form of high-intensity treatment. In this study, we are primarily identifying severe adverse events as deliberate self-harm, and suicidal ideation or attempts. Because of the risks involved, we will closely monitor, document, and report self-harm and suicide related behaviors (ideation or attempts) regardless if they are deemed related to treatment or not.

\*\*Next 4 topics not in Osiris\*\*

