#### **Unwanted events**

Unwanted events are defined as all events experienced as negative by the patient during treatment, which may or may not be related to the interventions being used, and does not necessarily influence treatment outcome, e.g., issues related to the treatment content, increased anxiety during exposure in vivo, and frustration caused by technical issues. Anxiety will be measured at regular follow-up points (3, 6, 12 months). Reported technical difficulties and our response to those technical difficulties will be recorded.

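### The adverse event definition requires probable attribution to treatment but names no assessor, and no section says the causality-free event categories reach the DSMB by arm

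*Protocol*

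**What the plan says.** Protocol 8.3 defines several kinds of negative effect. For adverse events it says: "Adverse events (AEs) consist of negative events probably emerging from treatment and perceived as adverse by the patient". The definition goes on to require worsening of target symptoms or an experience that outlasts treatment. During treatment, health coaches assess for rising negative affect; afterwards the GAD-7 is given at 3, 6 and 12 months.

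The severe category rests on timing and consequence: "negative events that occur during treatment and result in deterioration of target symptoms and/or adverse reactions requiring some form of high-intensity treatment". For one group of events causality is set aside outright: "we will closely monitor, document, and report self-harm and suicide related behaviors (ideation or attempts) regardless if they are deemed related to treatment or not".

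Three further categories in 8.3 need no causal judgement. Deterioration is followed by scores and coach check-ins. Novel symptoms are counted whether or not linked to treatment. The last is the broadest: "Unwanted events are defined as all events experienced as negative by the patient during treatment, which may or may not be related".

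On oversight, section 7.1 has the data coordinating center and the DSMB review, twice a year, "collected data (including adverse events, unanticipated problems, and subject withdrawals". The steering committee report in 6.2.1 (item 11) lists adverse events, serious adverse events and suspected unexpected serious reactions. Section 6.4 has the principal investigator look at outcome and adverse event data when weighing benefit against risk. The SAP contains no safety analysis.

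**The concern.** Whether an event happened and whether the program caused it are separate questions. Here the second must be answered before an event can be counted as an AE. The protocol does not say who answers it, on what scale, or with what knowledge of the arm.

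In a two-arm comparison this matters because attribution can differ between arms when occurrence does not. One of the protocol's own examples of an AE is heightened anxiety during CBT training, which points to one arm. A similar complaint in the Education arm may be less readily put down to the program and so not be labelled an AE. The explicit waiver for self-harm and suicide-related behaviour also suggests that relatedness does count for other AEs.

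At stake is how the DSMB, the steering committee or a later reader should interpret AE counts by arm. A difference could reflect expectation, a real difference could be hidden, and an event that nobody links to either program may not appear as an AE at all.

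**Working it through.** The plan gives no figure on this point, so there is nothing to reproduce. The check sets the definitions beside the reporting routes.

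| Category (Protocol 8.3) | Attribution required? | Collection described | Named as an oversight input? |
|---|---|---|---|
| Adverse events | Yes | Coach assessment; GAD-7 at 3, 6, 12 months | Yes: 6.2.1 item 11, 6.4, 7.1 |
| Severe adverse events | No general condition; waived outright for self-harm and suicidality | PHQ-9 item and suicide risk procedure | Yes: 6.2.1 item 11 |
| Deterioration | No | Scores, coach check-ins, monthly analysis of post-treatment data; target symptoms only | Not stated |
| Novel symptoms | No | None described | Not stated |
| Unwanted events | No | Scheduled anxiety scores; "Reported technical difficulties and our response to those technical difficulties will be recorded" | Not stated |

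**Who judges.** Section 8.3 names no assessor of causality. Coaches do the in-treatment assessment (8.3, under deterioration, adverse events and nonresponse). In the cCBT arm they reinforce CBT skills (6.1.1), and section 4.1 calls the trial open-label. The masking effort in 6.3 is directed at participants; no coach blinding is described. That coaches know the arm is therefore a sound inference, but it is not stated. Nor is it stated that coaches make the attribution.

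**Tracing one event.** Suppose a participant tells the coach about a new problem that is not self-harm, needs no high-intensity treatment, leaves pain and mood scores unchanged, and is not thought to come from the program. It is not an AE. It may be a novel symptom or an unwanted event, but no procedure described there would capture it, and no section gives it a route to the DSMB.

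**Reach of the waiver.** Under 8.2, people not affiliated with a participating clinical site "will only receive the PHQ-8 and will not be assessed for suicidality". Table 5 plans 50 enrolments through community organizations online; some of these may be affiliated with a site. For the unaffiliated, the waiver is not backed by the questionnaire screen.

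**Illustration only.** The arm size of 175 comes from Protocol 4.1; every rate below is assumed. Take at most one event per participant and the same true risk r in both arms.

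- Recorded AEs in an arm = 175 × r × a, where a is the chance that an event is attributed to treatment. The ratio between arms is a₁/a₂, whatever r is.
- With r = 0.30 there are 175 × 0.30 = 52.5 events per arm.
- a = 0.5 and 0.5: 26.25 against 26.25, ratio 1.
- a = 0.6 and 0.4: 31.5 against 21, ratio 1.5.
- a = 0.7 and 0.3: 36.75 against 15.75, ratio 2.33.

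In each case half of all events are not recorded as AEs, because the two rates average 0.5. For the chance that a two-sided 0.05 comparison of proportions would look significant, put p₁ = r·a₁, p₂ = r·a₂, p̄ their mean and n = 175:

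Φ{[|p₁ − p₂| − 1.96·√(2p̄(1 − p̄)/n)] / √([p₁(1 − p₁) + p₂(1 − p₂)]/n)}

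- 0.18 against 0.12: Φ[(0.06 − 0.0748)/0.0380] = Φ(−0.39) ≈ 35%.
- 0.21 against 0.09: Φ[(0.12 − 0.0748)/0.0376] = Φ(1.20) ≈ 89%.

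For r from 0.20 to 0.40 the range is 24% to 46% at 0.6/0.4 and 71% to 97% at 0.7/0.3. This shows that the mechanism could matter, not that it will operate.

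**The case against.** The strongest reply is that 8.3 should be read as a whole. It borrows a published scheme for internet and behavioral interventions in which the AE is one category among several, and the others need no attribution. A reader might infer that everything the DSMB sees has passed through a causality filter. The documents do not support that. Section 7.1 introduces its list with the word including, so the list is not exhaustive, and unanticipated problems and withdrawals carry no attribution test there. Severe events have no general attribution condition, and self-harm and suicidality are reported "regardless if they are deemed related to treatment or not".

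A reader might also infer that worsening in the Education arm would be lost. It would not: GAD-7 and PHQ-9 scores are collected electronically on the same schedule in both arms, the SAP models both by arm, and the check-in question given in 8.3 about worsening pain or mood is not arm-specific. What may be lost is the classification as an AE and any event the scales do not measure.

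Nor do the documents show that arm-aware coaches bias the count; as noted above, both steps are inferred. A drafting note left in 8.3 also points to another document for unexpected problems, the medical monitor and reporting times, and that document may say more. Finally, the trial is rated as minimal risk in 2.3.1, and the SAP plans no AE comparison by arm.

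These points narrow the concern. They do not supply an assessor, or a stated route to the DSMB for the categories that need no attribution.

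**Conclusion.** The concern holds in a limited form. The AE definition depends on an attribution that nobody is named to make, in an open-label trial. Events other than serious events and self-harm or suicide-related behaviour may therefore be counted as AEs selectively and differently by arm. The categories that could compensate have no stated tabulation by arm and no stated route to the DSMB.

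The size cannot be derived from the documents. The ratios of 1 to 2.33 above simply restate the assumed attribution rates and should not be read as estimates. The conclusion rests on the protocol text as it stands; the document behind the drafting note could change the reporting part of it. The change is worth making because it is cheap, but nothing here touches the primary efficacy comparison.

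**What to change.** 1. In 8.3, define an adverse event as a negative event during the study whether or not it is considered related to treatment. Elicit it with the same coach prompt in both arms; the existing check-in question is a starting point.
2. Record relatedness as a separate field, judged where possible by existing staff who are not told the arm.
3. Reconcile the new definition with unwanted events and novel symptoms, which it would overlap, so that each event is counted once.
4. State in 7.1 that all 8.3 categories go to the DSMB by arm, with the related subset shown alongside. If the document behind the drafting note already covers part of this, bring that text into 8.3.
5. Do not let site records replace event reporting for participants who are not affiliated with a clinical site. Their records are used only to confirm the diagnosis (Protocol 4.1, Medical Outcomes; SAP, Medical Outcomes). Table 4 also places health care utilization at month 12 only, while the DSMB review is semi-annual.

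The cost is protocol and case report form wording, one added field, and more events to log and classify among 350 people with chronic pain, including staff time for the relatedness judgement. Randomization, treatment and the efficacy analyses are unchanged.
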